We propose an integrated and coordinated pathway from the ED to gout continuity of care through primary care and specialty providers. We will leverage innovative recruitment and retention strategies that utilize lay patient navigators at our UAB site, a strategy that was successfully pioneered at UAB by our MHDRC team led by [name] for medical care and research in other disciplines including oncology.^{48, 69-71} Patients classified as having gout based on the 2015 ACR/EULAR criteria^{77, 78} who meet the inclusion/exclusion criteria (noted below) will be randomized 2:1 stratified by race/ethnicity, to the intervention or control arm of this demonstration study. **Figure 1** provides an overview of the study design.

Figure 1. Improving ED Gout Care- Study Design

B.2 Patient Population

B.2.1 Key inclusion criteria

- Meets Gaffo criteria for current gout flare or ED physician diagnosis of acute gout flare
- Adult > 18 years of age,
- Able to communicate and understand English language (a future objective, with additional resources, will include Spanish translation of all study materials).
-

B.2.2 Key exclusion criteria:

- joint complaint related to significant trauma or recent surgery (< 1 month)
- life expectancy of < 6 months,
- current critical illness leading to admission to high acuity medical care unit (ICU, stepdown unit) or requiring surgical intervention (general anesthesia); confirmed septic arthritis or joint infectious arthritis.

B.3 Gout Alert Development and Validation (Aim 1)

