A lay patient navigator working with and trained by the UAB MHRC and the gout research team will contact patients seen in the UAB ED via phone within 72 hours following the ED visit. During this initial phone conversation the navigators will: 1) conduct a baseline assessment to identify barriers to attending an outpatient visit for gout care (e.g. transportation) and to adhering to gout treatment recommendations (medications, diet, exercise) and, 2) determine the level of support and assistance (e.g. transportation support) needed by patient. The patient navigator will help facilitate the follow-up visit with a primary care/gout specialist, identify any barriers (e.g. lack of trust in primary care physician or/and healthcare system),⁸² and provide institutional/community resources that can be mobilized for the patient. The navigator will conduct two additional follow-up calls at approximately one month and at one week (anticipated) prior to the visit to confirm the appointment time, the level of support needed (as needs may have changed), and encourage him/her to keep their appointment. In the unlikely event that the appointment with the PCP/gout specialist is sooner than one month, this one-month pre-appointment call will be eliminated and the navigator will have only two calls with the patient (**Figure 2**). Navigators will be trained using didactic materials, including case simulations and role-play, that will be prepared as part of this study. Participants at all sites will be provided a card with a group picture of the patient navigator team that will contact them.

Figure 2. Study Workflow – Patient Navigation

B.5.3 Usual Care Arm -ED Encounter.

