Similar to the intervention arm patients randomized to the control arm at both institutions will be provided with a follow usual care referral to relevant medical services that might benefit their gout under their existing health plan, such as primary care services (if they do not already have a primary care physician) or to the Cahaba Medical Group at the UAB Site. Timing for this planned follow-up will be consistent with typical wait times to see a specialist or general practitioner for their gout. In most US metropolitan areas, given the limited national supply of rheumatologists, the average wait time is 9 to 10 weeks to see a new patient.⁸³ To address the issue of an “attention control,” all persons randomized to the control arm will receive existing educational e-material on the tablet computer on routine preventive health measures including vaccinations and age-appropriate preventive care measures unrelated to gout or the study outcomes. These materials will also be emailed to them.

B.5.4 Gout CORT Registry and Biorepository Sample Collection (Aim 3)

Blood specimens and synovial fluid (if drawn) will be collected for the Gout CORT Registry and Biorepository at the time of the enrollment visit in the ED. Blood specimens and synovial fluid (if collected as part of ED visit) will be collected by ED study coordinators/RAs in PAXGene RNA/DNA tubes and stored in -80° freezer until transport to the UAB Division of Clinical Immunology and Rheumatology for processing and long-term storage (see Shipping Manual). All samples will be labeled with a patient identification (PID) number and date of visit. Documentation of specimens will be stored in the lab computer database, secured and password protected, and distributed to only to authorized personnel. Banked specimens will be available for future research in gout, hyperuricemia, and gout-comorbid conditions (e.g. hypertension, diabetes) and will include samples for genomic DNA, RNA expression, and epigenetic analysis.

B.6 Informed Consent (IC)

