Secondary Outcomes / Covariates				
Social Determinants of Health				
Environmental and social factors	X			
Gout medical care				
Number of gout flares (Gaffo criteria) ^{79, 84}	X	X	X	
Rates of urate lowering therapy (ULT)**	X	X	X	
ULT adherence		X	X	
Opioid prescriptions*	X	X	X	
Weight reduction		X	X	
Healthcare resource utilization (visit number)				
ED visits (indicative of recidivism)*		X	X	
Hospitalizations*		X	X	
Health-related quality of life				
European Quality of Life (EQ-5D) ⁸⁶⁻⁸⁸	X	X	X	
Shared decision making: CollaboRATE scale ⁹⁰		X	X	

* gout follow-up within 3-months of ED visit. ** Assessed through chart or system review

randomized 2:1 stratified by race/ethnicity, to the intervention (storytelling +/- patient navigation) or control arm (usual care). All intervention arm patients in the UAB ED also will be assigned lay navigators to provide personalized support for care transitions and access to post-gout flare medical services needed for preventing recurrent flares.

The following procedures will be completed during the index ED visit:

- Review inclusion/exclusion criteria for registry participation
- Informed Consent
- Review of current/past gout status and medication chart review
- Pain Assessment
- Laboratory
 - Serum uric acid (from chart review)
 - Sample banking
- Survey assessments
 - HRQL
 - SDOH

Laboratory draw will be done in conjunction with ED care blood draw when possible. At the conclusion of visit, participants randomized to navigator arm will be provided navigators picture, contact information, and informed that they will receive a call w/in 72 hours.

B.9.1.2 *Patient Navigator Contact*

72 hours post ED visit

During this initial phone conversation the navigators will: 1) conduct a baseline assessment to identify barriers to attending an outpatient visit for gout care (e.g. transportation) and to adhering to gout treatment recommendations (medications, diet, exercise) and, 2) determine the level of support and assistance (e.g. transportation support) needed by patient. The patient navigator will help facilitate the follow-up visit with a primary care/gout specialist, identify any barriers (e.g. lack of trust in primary care physician or/and healthcare system), and provide institutional/community resources that can be mobilized for the patient.

4 weeks post ED visit and 24-48 hours prior to appointment (anticipated)

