Outcome ascertainment	X			X	X
Study debriefing				X	
Assess AEs			X	X	X

[°]Primary outcome assessment will occur at any point upto 6 weeks post ED visit dependent on routine care visit; # For individuals randomized to navigation arm; ^{\$}Navigator will contact participant in the week prior to scheduled follow-up visit

B.9.1.6 **Blinding and Unblinding**

Participants will blinded to study assignment at enrollment, and following primary outcome ascertainment will be debriefed regarding the study and its purpose/goals.

B.10 Statistical Analysis Plan

B.10.1 Primary Outcome Analysis - Aim 1.

All analyses will adhere to the principles of rigor, reproducibility and transparency.^{109, 110} To determine the effectiveness of our alert system, we will examine the diagnostic properties (sensitivity/specificity) of the EMR alerts against a gold standard of NLP/ML detection (section C.4.2)

B.10.2 Primary Outcome Analysis- Aim 2.

Descriptive statistics, including measures of central tendency (means for continuous, proportions for categorical) and dispersion (variance, interquartile range) will summarize the distribution of baseline characteristics of randomized patients seen in both EDs. Descriptive statistics will be summarized by treatment arm as well as enrollment site. These statistics will inform the successfulness of randomization in creating comparable groups and ascertain our success in recruiting the populations we seek to target (particularly under-represented minorities). We also will compare the descriptive characteristics between those participants who do and don't respond to follow-up surveys to detect and report any evidence of a selective non-response bias. The primary analysis approach for testing treatment effect will be a multivariable logistic regression

model. We have chosen multivariable logistic regression over Cochran-Mantel-Haenszel approaches to allow for effect estimation of multiple covariates (race, gender, age) upon the primary outcome and to allow tests of interactions. Logistic regression models, including interaction terms, will be developed for 6 week outcomes and 3 month outcomes. We will examine the significance of the effects of the intervention as the outcome of persons receiving at least one outpatient gout follow-up visit at 3 months. We will analyze rates on an intent-to-treat basis for the primary analysis. We will conduct all analyses using SAS 9.4 (Cary, NC)

[figure not shown]

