B.10.3 Secondary Outcome Analyses- Aim 2.

Patient reported outcomes (PROs) and other process of care measures are of key interest in this study. We will examine secondary outcomes using either two-sample t-tests or multiple linear regression models. Distributional assumptions for residuals (normality, homogeneity of variance) will be examined using normal probability plots and residual plots. We will conduct a set of stratified analyses (contrasts) to examine how the between-site differences in approaches affect outcomes. First, comparing across control arms at the four sites we can estimate the impact of the intervention. Second, comparing across intervention arms at the four sites, we can estimate the difference attributable to case manager versus navigators when all individuals receive story telling. We will also examine sex as a biological variable as well as effects of age and race/ethnicity (heterogeneity of treatment effect). We will conduct sensitivity analyses using multiple imputations to account for missing data. While we provide an example sample size for one such measure, the evaluation of these endpoints will be hypothesis-generating only.

B.11 Sample Size Considerations for Aim 2

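### The two between-site contrasts in B.10.3 cannot estimate the intervention effect or a case-manager-versus-navigator effect

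*Combined protocol and SAP*

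**What the plan says.** Section B.10.3 (Secondary Outcome Analyses, Aim 2) sets out stratified contrasts meant to show how differences in approach between sites affect outcomes. The first is described this way: "comparing across control arms at the four sites we can estimate the impact of the intervention". The second compares intervention arms across the four sites, from which "we can estimate the difference attributable to case manager versus navigators when all individuals receive story telling". The section ends by saying that "the evaluation of these endpoints will be hypothesis-generating only".

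Randomisation (B.1, under Aims 1 and 2, and B.9.1.1) is 2:1 to intervention or usual care, stratified by race/ethnicity. Type of support is not randomised, and site is not named as a stratum. Under B.5.3, controls receive a usual-care referral plus tablet material on vaccination and "age-appropriate preventive care measures unrelated to gout or the study outcomes".

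On who receives navigation, the protocol says different things:

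- B.1, Aims 1 and 2: "innovative recruitment and retention strategies that utilize lay patient navigators at our UAB site".
- B.5.2: the navigator telephones patients seen in the UAB ED, yet "Participants at all sites will be provided a card with a group picture of the patient navigator team that will contact them".
- B.9.1.1: patients are randomised "to the intervention (storytelling +/- patient navigation) or control arm (usual care", and UAB intervention patients are assigned navigators.
- Visit schedule in B.9.1.5, footnote: "For individuals randomized to navigation arm", although no separate navigation arm is defined.
- D.2: navigation is listed as a study intervention visit at UAB, MGH, MetroHealth and Iowa.

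**The concern.** An intervention effect needs treated and untreated patients in the same comparison. The first contrast has only untreated ones, so whatever it returns is a difference in usual care, case mix or reporting between hospitals. An analyst who followed the sentence would report that as the impact of the intervention.

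The second contrast has only treated patients and attributes their differences between hospitals to the type of support. Hospitals differ in many other ways, and nobody was randomised to a type of support. The term case manager appears only in this sentence of the text available; no role, site, training or contact schedule is given. The protocol's conflicting statements on navigation also leave it unclear whether the sites differ in support at all.

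**Working it through.** **The plan's own figure.** The only power statement concerns the primary comparison (B.11): 200 patients, 2:1, control rate 30%, relative risk 1.68, two-sided 0.05, 80% power. A pooled two-proportion calculation gives 79.4%, so it reproduces. No figure is stated for the B.10.3 contrasts.

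**What each contrast measures.** Let c be the control rate and δ the within-site effect, with subscripts U for UAB and O for the other sites.

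- Contrast 1 = c_U − c_O. There is no δ in it.
- Contrast 2 = (c_U + δ_U) − (c_O + δ_O) = (c_U − c_O) + (δ_U − δ_O). The site difference in control rates is carried in full.
- Contrast 2 − contrast 1 = δ_U − δ_O, the treatment-by-site difference.

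The design matrices agree:

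| Patients used | Terms | Rank |
|---|---|---|
| Controls only | 4 sites + treatment | 4 of 5 |
| Intervention only, navigators at UAB only | 4 sites + navigator | 4 of 5 |
| Intervention only, navigators at all sites | 4 sites + navigator | 4 of 5 |
| Both arms | 4 sites + treatment + treatment × UAB | 6 of 6 |

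In the first row the treatment column is all zeros. In the second the navigator column equals the UAB indicator. In the third it is constant. No sample size cures these.

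**Insensitivity of contrast 1.** With a 30% control rate at every site, the within-site difference is 0.30 × (RR − 1): 0, 9 and 20.4 points at relative risks of 1.0, 1.3 and 1.68. The expected value of contrast 1 is 0 in all three cases.

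**How contrast 2 could mislead.** The documents give no site-specific rates, so this rests on assumptions: other-site controls at 30%, UAB controls 5, 10 or 15 points higher, relative risk 1.68 at every site, no support-type effect. Section D plans 168 patients at UAB and 112 elsewhere. With 2:1 allocation and the 30% non-response in B.11, responders are:

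- UAB: 168 × 2/3 × 0.7 ≈ 78 intervention and 168/3 × 0.7 ≈ 39 control
- Other sites: 112 × 2/3 × 0.7 ≈ 52 intervention and 112/3 × 0.7 ≈ 26 control

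| UAB control excess | Contrast 1 expected | Contrast 2 expected (excess × 1.68) | Contrast 2 significant |
|---|---|---|---|
| 5 points | 5 | 8.4 | about 16% |
| 10 points | 10 | 16.8 | about 48% |
| 15 points | 15 | 25.2 | about 84% |

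All of contrast 2 here comes from the site difference in control rates.

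**Precision, UAB versus the other sites pooled** (rates 30% and 50.4%, so variances 0.21 and 0.25):

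- Contrast 1: SE = √[0.21(1/39 + 1/26)] = 0.116; 95% half-width about 23 points.
- Contrast 2: SE = √[0.25(1/78 + 1/52)] = 0.0895; half-width about 18 points.
- Treatment-by-site difference: SE = √(0.21/39 + 0.25/78 + 0.21/26 + 0.25/52) = 0.1465. Detectable with 80% power: 0.1465 × (1.960 + 0.842) = 0.41, or 41 points.
- With full response (56/112 at UAB, 37/75 elsewhere): SE 0.122, detectable 34 points.

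For a continuous outcome in SD units, the half-widths are 0.50 and 0.35. The detectable treatment-by-site difference is 0.87, or 0.73 with full response.

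**The case against.** The strongest reply is that little hangs on these sentences. The randomised comparison is already planned: B.10.2 has an intention-to-treat logistic model that allows interaction tests, and B.10.3 opens with t-tests or linear regression for secondary outcomes. Contrast 1 may be a drafting slip. Read as a pair, the contrasts are also close to something useful, since their difference is the treatment-by-site effect. That stands as a limit on the consequence. It does not rescue the wording: the plan never says the two will be subtracted, and it gives each its own causal reading. The hypothesis-generating label covers imprecision and multiplicity, but it does not make a quantity estimable.

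A second reply is that case managers may have been intended at one or more sites other than UAB. The text retains traces of a two-centre design (Vanderbilt is named in the opening of section D, and B.10.2 and F.4 refer to two centres), and the figures and step-by-step guide are not available here. This is plausible, and contrast 2 would then compare two real approaches. It would still be non-randomised and confounded with site.

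A third reply is that some of the navigation passages are compatible. The footnote may be shorthand for the intervention arm, and the plus-or-minus wording fits navigation at UAB only. That is fair. The firm conflict is between B.1 and B.9.1.1 on one side and D.2 and the card sentence in B.5.2 on the other. That conflict also bears on what the pooled primary effect means: if only UAB navigates, the effect averages storytelling with navigation and storytelling without it. The primary test remains valid, but its interpretation depends on the answer.

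Finally, the precision figures pool three sites and borrow primary-outcome rates. Comparing four sites separately is worse. If the 112 are split equally, each other site has about 9 control responders. The contrast 1 half-width is then about 33 points for UAB against one other site (39 v 9), and about 42 points for two other sites (9 v 9). The flaw is one of identification and does not depend on these figures.

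**Conclusion.** The concern holds. Contrast 1 carries no information about the intervention at any sample size. Contrast 2 does not identify a case-manager-versus-navigator effect on any reading: if all sites navigate there is nothing to compare; if only UAB does, it compares navigators with no navigators; if case managers work elsewhere, support type is still confounded with site.

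The size of the bias cannot be computed, because the documents give no site-specific rates. The 16%, 48% and 84% figures illustrate assumed site gaps; they are not predictions. The detectable treatment-by-site difference of about 41 points assumes 2:1 allocation within site, 70% response and the B.11 rates.

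The error is confined to analyses labelled hypothesis-generating; the primary test and its power statement are untouched. It should be corrected because, followed as written, it would present hospital differences as treatment effects.

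**What to change.** 1. Replace contrast 1 with intervention minus control within site, combined by stratifying on or adjusting for site. If a control-arm comparison is kept, label it as a description of usual care by site.
2. Replace or relabel contrast 2 as a descriptive treatment-by-site estimate (UAB versus other), reported with a confidence interval and not as a test. State that the within-site effects are randomised, that any difference between sites in effect remains confounded with site, and that precision is low. State the effect scale too: in the illustration with a 10-point control gap, a constant relative risk of 1.68 still gives a 6.8-point difference in risk differences (16.8 − 10).
3. Define case manager, with site and role, or remove the term.
4. Reconcile B.1 (Aims 1 and 2), B.5.2, B.9.1.1, the B.9.1.5 footnote, B.10.3 and D.2 on which sites and patients receive navigation, so that the content of the intervention at each site is clear.

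The cost is wording plus one small exploratory model on data already being collected. The primary analysis, sample size and data collection do not change. The new model cannot separate mode of support from site, and the text should say so.

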Patients and study coordinators will enter baseline demographic, gout history, patient reported outcomes (PROs) directly into electronic case report forms into a 21CFR and HIPAA compliant REDCap (Nashville, Tennessee) system. We will host REDCap on one of several access-controlled, encrypted servers housed at UAB. Subsequent PROs and other outcome data will be captured by phone in the same REDCap database by the study teams. Baseline laboratory data and medication data will be obtained from our respective EMRs and will be reviewed during the phone calls and by the research assistant during the ED visit.

B.8 Study Outcomes

Study outcomes (**Table 2**) will be collected from patients at 6 weeks and 3 months following the initial ED visit with questionnaires deployed using computer assisted telephone interviews (CATI) programmed in REDCap. Validated items about gout flares and gout medications have been used in the past by our team.⁸⁴

B.8.1 Primary outcomes Aim 1 and 2.

The primary outcome of aim 1 will be the ability of the alert to successfully identify gout patients. For aim 2, it will be the proportion of patients that have a follow-up visit addressing gout in the 3-month period after the ED visit. Many gout patients are not adherent with their follow-up visits due to a lack of awareness of the consequences of untreated

gout, poor care access, and/or inadequate assistance to obtain a follow up visit. Even rapidly-scheduled outpatient visits (next business day) following an ED encounter are only attended by 73% of those seen in a recent study and rates of post-ED follow-up for many chronic disease are closer to 50%.^{91, 92} Moreover, most patients, ~80%, leave the ED with knowledge deficits that impact adherence and outcomes.^{93, 94} Having a usual source of primary care and establishing continuity of care after an ED visit is critical to optimal disease outcomes in all chronic diseases including gout.³⁰⁻³² This data will be captured both by self-report on surveys (this will be the primary study outcome) and by review of EMR data within our respective healthcare systems. While self-report will be impacted by recall and possible social desirability bias, this should be non-differential (bias towards the null).⁹⁵ EMR data will be more accurate for some outcomes but will miss any gout care delivered outside our urban Southeastern medical centers and their satellite facilities.

B.8.1.1 Secondary outcomes - Aim 2

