The navigator will conduct two additional follow-up calls at approximately one month (4 weeks) and in the week (anticipated) prior to their visit to confirm the appointment time, the level of support needed (as needs may have changed), and encourage him/her to keep their appointment. In the unlikely event that the appointment with the PCP/gout specialist is sooner than one month, this one-month pre-appointment call will be eliminated and the navigator will have only two calls with the patient.

B.9.1.3 *6 Week Follow-up Assessment*

At 6 weeks following ED visit, participants will be contacted by the Coordinating Center (CC) to to assess project outcomes via a telephone survey. The following information will be collected, and data collected via the surveys and EMR. Following completion of the follow-up surveys the study coordinator will inform and debrief the patient that they participated in a study evaluating methods to improve continuity of gout care. The debrief will be conducted after the 1st survey. If RA the coordinator is unable to reach participant on the phone, the survey questions used to collect the primary outcomes will be sent via email or text messaging using Mosio, which is an HIPAA-compliant application.

- Survey assessments
 - Patient satisfaction
 - HRQL
 - PROs
- Updated medical history and review of concomitant medications
- Assessment of Adverse Events (AEs) (as meeting NIH definition of Phase III study AEs will be collected)

B.9.1.4 *3 Month Follow-up Assessment*

At 3 months (anticipated) post ED visit participants will be contacted to complete a second follow-up survey and end of study (EOS) via telephone to assess secondary outcomes (e.g. adherence to orders, medication RX, and labs (if ordered)).

- Survey assessments
 - Patient satisfaction
 - HRQL
 - PROs
- Updated medical history and review of concomitant medications
- Assessment of Adverse Events (AEs) (as meeting NIH definition of Phase III study AEs will be collected)

B.9.1.5 **Table 1 Visit Schedule**

Visit description / Study procedures	Screening and Enrollment (ED)	V1 (phone)	V2 (phone)	V3	V4 EOS
	Day 0	72 Hours	4 WK	6 WK [°]	3 MO
Review of Inclusion/exclusion criteria following alert notification	X				
Informed consent for INSIGHT Registry	X				
Medical history	X				
Laboratory					
SUA	X				
Sample banking	X				
Randomization	X				
Patient Navigator Contact#		X	X ^{\$}	X ^{\$}	
Updated medical history and concomitant medications		X	X	X	X

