As this study meets the NIH definition of a clinical trial, and as outlined in our data safety monitor plan we will collect information including diagnosis errors and participant anxiety from answering questions about their health status. All AEs will be captured on the appropriate electronic case report form.

An **Adverse Event (AE)** is defined as any untoward medical occurrence in a participant who received study intervention regardless of its relationship to the study intervention. This determination will be made by the study

principal investigator. Preexisting conditions will not be considered adverse events; however, worsening of a preexisting condition may be considered an AE. AEs will be assessed as to their relationship to the research, severity, and duration. They will be documented appropriately, regardless of the relationship, with start dates occurring any time after informed consent until 7 days after the last day of study participation. AEs will be reported in aggregate to the Safety Officer (SO), Institutional Review Board (IRB) and NIAMS (through the Executive Secretary) as part of the routine safety report.

A Serious Adverse Events (SAE) is any AE that results in death, is life-threatening, results in or prolongs hospitalization, or causes a permanent, persistent or significant disability. SAEs will be reported to the SO, IRB, and NIAMS (Executive Secretary) within 48 hours of the investigator becoming aware of the event. All SAEs will be followed until satisfactory resolution or until the site investigator deems the event to be chronic or the participant is stable.

An Unanticipated Problem (UP) includes any incident, experience, or outcome that is unexpected and possibly related to participation in the research. UPs will be reported to the SO, IRB and NIAMS (Executive Secretary) within 48 hours of the investigator becoming aware of the event.

A protocol deviation is defined as any substantial divergence from the IRB-approved study protocol. Any protocol deviation impacting patient safety will be reported to the SO, IRB and NIAMS (Executive Secretary) within 48 hours of the investigator becoming aware of the event; all other deviations will be reported as a part of the routine safety report.

For additional details see Data Safety Monitoring Plan.

D. Study Sites

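### No adverse-event assessment is scheduled in the ED and no step is given for finding revised index diagnoses, so a low count of either named harm would not show that it is rare

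*Combined protocol and SAP*

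**What the plan says.** Section C (Adverse Events) names two harms: "we will collect information including diagnosis errors and participant anxiety from answering questions about their health status". It attributes this to a data safety monitoring plan and refers to that plan again for further detail. AEs count "with start dates occurring any time after informed consent until 7 days after the last day of study participation", and are defined as "any untoward medical occurrence in a participant who received study intervention regardless of its relationship to the study intervention".

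The AE-assessment row of the visit schedule (B.9.1.5) has three marks, at 4 weeks, 6 weeks and 3 months, and nothing at Day 0 or 72 hours. The visit text lists "Assessment of Adverse Events (AEs) (as meeting NIH definition of Phase III study AEs will be collected" at 6 weeks (B.9.1.3) and 3 months (B.9.1.4) only. The ED list in B.9.1.1, introduced by "The following procedures will be completed during the index ED visit", includes a pain assessment and the quality-of-life and social-determinants surveys, but no AE assessment.

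B.2.1 accepts either the flare criteria or the ED physician's diagnosis for entry. B.2.2 excludes "confirmed septic arthritis or joint infectious arthritis". B.8.1 plans to capture follow-up visits by survey and also "by review of EMR data within our respective healthcare systems".

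**The concern.** The two harms arise where the AE schedule is weakest. Distress from the first set of health questions would arise in the ED while study staff are with the patient, yet the first scheduled AE question comes weeks later, when brief distress is poorly recalled. A diagnosis error is mainly visible in the chart. Entry can rest on an ED diagnosis, and only confirmed joint infection is excluded, so a later result or visit can change the diagnosis. Nothing in the supplied text tells staff to look for that in enrolled patients.

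The safety report goes to the Safety Officer, the IRB and the funder. A small number in it could be read as reassurance when it may only reflect that few patients were asked at the right time or in the right way. The number of revised index diagnoses also helps in reading Aim 2, whose outcome is a visit addressing gout.

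**Working it through.** The plan states no expected count, rate or capture probability for either harm, so there is no figure to reproduce. The check compares the sections.

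**1. Survey occasions against AE assessments**

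| Occasion | Health questions asked | AE assessment scheduled |
|---|---|---|
| ED, Day 0 (B.9.1.1) | Yes | No |
| 6 weeks (B.9.1.3) | Yes | Yes |
| 3 months (B.9.1.4) | Yes | Yes |

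Two of three coincide; the ED occasion is the gap. If the 6-week call fails, B.9.1.3 sends only the primary-outcome questions by email or text and mentions no AE items.

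**2. Week 4.** The schedule marks an AE assessment at 4 weeks and the visit text does not. The only week-4 study contact described in the text is the navigator call (B.9.1.2), and the schedule footnotes the navigator row "For individuals randomized to navigation arm". The AE row carries no such limit. If AEs are asked on that call, the intervention arm has an AE contact that controls lack. If they are not, table and text disagree. With 2:1 allocation of 280 patients, controls number about 280/3 = 93 and intervention patients about 187.

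**3. Diagnosis errors.** Consent follows apparent eligibility (B.6), so an erroneous index diagnosis can predate the AE window. It is unclear whether an error counts as an AE under the Section C definition, and that definition refers to those who received study intervention, which leaves control coverage unclear. No reference standard or abstraction item for enrolled patients appears in B.8, B.9, B.10 or Section C. In contrast, the Aim 1 chart sample has two rheumatologist reviewers and an adjudicator (B.3.2).

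**4. Why a low count is ambiguous.** Expected reports = 280 × true rate × capture probability. True rates and the 10% capture are assumptions. The 70% capture reflects only the 30% survey non-response that B.11 expects at 3 months (280 × 0.30 = 84 not answering, 196 answering).

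| Assumed true rate | Cases in 280 | Reports at 70% capture | Reports at 10% capture |
|---|---|---|---|
| 1% | 2.8 | 2.0 | 0.3 |
| 5% | 14 | 9.8 | 1.4 |
| 10% | 28 | 19.6 | 2.8 |

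A report of about two cases fits a 1% rate with good capture, or a 5% to 10% rate with poor capture. If none were reported, the one-sided 95% upper bound would be 1 − 0.05^(1/280) = 1.1%, or 1 − 0.05^(1/196) = 1.5% among 196. Either bound is valid only if every patient counted was actually asked or checked.

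**The case against.** The strongest objection is that Section C assigns these items to a Data Safety Monitoring Plan that is not among the documents. That plan may contain the method, so the defect can only be stated as not specified in the protocol and visit schedule. This stands.

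Several other points also stand:

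- Day 0 distress after consent is inside the onset window and can still be reported later.
- Medical history is updated at follow-up, the 6-week data come partly from the EMR, and Section C does not restrict collection of diagnosis errors to a telephone AE question. A revised diagnosis could surface by these routes, although nothing directs staff to look for one.
- D.3 lists AE monitoring among activities carried out weekly or more often. The list is generic, but AE capture is not stated to be confined to the marked cells.

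A reader might infer that both harms fall wholly outside the AE assessments. They do not: the 6-week and 3-month questionnaires coincide with one. A reader might also infer that every control waits at least 42 days for a first AE question. The documents do not support that: the table marks AEs at 4 weeks without restricting that row to one arm, a footnote to the 6-week column allows primary outcome assessment at any time up to 6 weeks, and enrolment may follow presentation by up to 48 hours.

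**Conclusion.** The point holds in a limited form. No AE assessment is scheduled on the ED day, and the supplied documents give no case-finding step for revised index diagnoses in Aim 2 patients. A low reported count of either harm would therefore not show that it is rare. The gap is one of three survey occasions for questionnaire distress, and an undefined item for diagnosis errors. The conclusion rests on the supplied text and could be softened by the Data Safety Monitoring Plan.

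Three stronger conclusions are tempting and unsupported:

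- That counts will be near zero. No capture probability is given. In the illustration, near-zero reporting at true rates of 5% to 10% needs capture of about 10% or less, which the documents neither state nor exclude.
- That Aim 2 loses a calculable amount of power. No revision rate is given, a patient whose index flare is relabelled may still have gout and a gout visit, and counting revisions would not restore power.
- That the AE window should be cut back because no assessment covers its last 7 days. Spontaneous or chart-detected events can still be recorded then, and shortening the window would reduce safety coverage.

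**What to change.** 1. In the B.9.1.5 schedule, add a Day 0 mark to the AE-assessment row, and list the assessment in B.9.1.1. After the ED questionnaires, the research assistant asks patients in both arms about distress and records the answer on the existing electronic case report form.
2. In the EMR review already planned under B.8.1, record for every randomised patient in both arms whether the index diagnosis was later revised. Report the count and proportion with a confidence interval, described as a lower bound because care outside the participating systems is missed.
3. Reconcile the week-4 AE mark in the schedule with the visit text, and make any week-4 AE contact the same in both arms.

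If the Data Safety Monitoring Plan already defines either step, cite it in Section C and align the schedule with it. The cost is a few minutes per patient, one extra abstracted field and a table edit. These changes affect ascertainment only, not the intervention or clinical care.
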